- Secondary outcome 3: What is the impact of the “Putting the Kitbags to work” programme on the **stress** (as measured by the “Stress in General” scale) of social workers and family support workers in teams randomly allocated to the intervention arm compared with social workers and family support workers in teams randomly allocated to the control arm? The outcome will be measured at month 6 and month 13 after intervention began.
- Secondary outcome 4: What is the impact of the “Putting the Kitbags to work” programme on the **number of sick days** taken by social workers and family support workers in teams randomly allocated to the intervention arm compared with social workers and family support workers in teams randomly allocated to the control arm from T1 to T13?

Foster carer outcomes:

- Secondary outcome 5: What is the impact of the “Putting the Kitbags to work” programme on the **self-efficacy** of foster and kinship carers supported by social worker teams randomly allocated to the intervention arm compared with foster carers supported by social worker teams randomly allocated to the control arm as measured? The outcome will be measured at month 6 and month 13 after intervention began. The population will be restricted to local authority employed foster carers only..

Design

Trial type and number of arms	Parallel multi-site cluster RCT (2 arms)
Unit of randomisation	Social Work Team (6-8 social workers)
Stratification variables (if applicable)	Local authority and team type (CIN+CP/CLA/Children with disabilities)

Participants

Oxfordshire County Council, the London Borough of Bexley, Haringey Council and Warwickshire County Council shall be participating in the trial.

Teams

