Since the intervention is allocated by team, we define eligibility criteria for teams: statutory teams who we would typically expect to conduct longer term (4+ months) work with children and young people to allow for the minimum number of sessions with a Kitbag. This includes safeguarding teams who work with child and young people who are subject to a child in need (CIN) plan or a child protection plan (CPP), teams that work with children who are looked after (CLA) or teams who work with children with disabilities. Please see Table 1 for the number of eligible teams per local authority. As different local authorities have slightly different names for each team, we've included the type of team in brackets. The teams we have determined are not eligible to participate therefore, are MASH / front door, assessment, early help, youth justice and leaving care teams as they do less of the longer term direct work. Please see Table 2 for the number of social workers, family support workers and foster carers.

Table 1: Eligible teams within each local authority

Local authority	Eligible teams
Bexley	Family support and child protection teams (North, East, Central and South, South West) (4 CIN / CPP teams) Looked After Children team (1, 2, 3) (3 CLA teams) Children with Disabilities team (1, 2) (2 Children with disabilities teams) Total: 9 eligible teams
Haringey	Children in Care team (1, 2) (2 CLA team) Disabled Children's team (1, 2) (2 Children with disabilities teams) Safeguarding and Support team (1-6) (6 CIN / CPP teams) No Recourse to Public Funds team (1 CIN / CPP teams) Total: 11 eligible teams
Oxfordshire	Children's Disability Teams (North, South, City) (3 Children with disabilities teams) Family Solutions Plus Teams (North 1-6, Central 1-5, South 1-6) (17 CIN / CPP teams) Rosehill Statutory Teams (1, 2) (2 CIN / CPP teams) Unaccompanied Children (1 CLA team) Children in Care (North 1, North 2, South 1, South 2, Central 1a, Central 1b, Central 2) (7 CLA teams) Total: 30 eligible teams
Warwickshire	Safeguarding and support (Bedworth and North Warwickshire, Nuneaton, Rugby, Stratford, Warwick) (5 CIN / CPP teams) Children in Care aged 14-18 (1 CLA teams) Strengthening Families (1 CIN / CPP team) Children with Disabilities (safeguarding and support hub, children in need hub, strengthening families hub) (3 Children with disabilities teams) Total: 10 eligible teams
Total	60

Social workers and family support workers

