Local authority	Number of social workers and family support workers in teams in the intervention group	Hold back for staff turnover (assume 15%)	Number of foster carers (including kinship carers) in the intervention group	Hold back for new foster carers (assume 10%)	Number of Kitbags for social workers in the fostering service	Total
Bexley	33	5	57	6	2	103
Haringey	28	4	100	10	2	144
Oxfordshire	120	18	119	12	4	273
Warwickshire	119	18	148	15	10	310
Total	300	45	424	43	18	830

Children and young people

Children and young people aged 4-18 years old who have an open case in May 2021 or whose case opens between May 2021 and December 2021 and supported by social workers and family support workers in eligible teams are eligible for the programme. Only those whose

case starts before December 2021 will be eligible to allow for the minimum number of sessions to feasibly be delivered with a Kitbag before the evaluation period concludes (May 2022).

The number of children and young people who are classified as children in need (according to the Department for Education’s broad definition including children on a child in need plan, child protection plan and children in care) across these four local authorities is approximately 13,000. We estimate that there are approximately 9300 eligible children and young people across the four local authorities (henceforth we refer to them as the population).⁶

Table 3: Number of children in need in Bexley, Haringey, Oxfordshire and Warwickshire between 2019 and 2020

Local authority	Number of children in need at 31 March (2019)	Number of children in need at 31 March (2020)
Bexley	1594	1757
Haringey	2073	2284
Oxfordshire	4511	4750
Warwickshire	3914	4073
Total	12092	12864

Recruitment

Social workers / family support workers

Social workers will be identified from their membership in eligible teams, as per the HR IT systems of the local authorities. The social workers and family support workers will be asked to provide their informed consent before participating in the primary data collection (survey, interviews). They will also be notified of the use of their absence data in the email inviting them to participate in the survey at T6 (prior to the data sharing) and of their rights in relation to the processing.

Children and young people

Children and young people will be identified as eligible by their allocation to a social worker in an eligible team.

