If the sample is imbalanced with respect to team type (CIN / CP, CLA, children with disabilities) within the local authority, we will re-randomise (setting a new seed). We take imbalance to be the proportion of teams of that type within the local authority assigned to the intervention to be greater than 0.75 or less than 0.25 (i.e. $\frac{3}{4}$ or $\frac{1}{4}$ teams) except where there is only one team of that type in the local authority.

We will also report the mean proportion of social workers to family support workers, and the mean proportion of permanent staff to agency staff, by treatment allocation but will not re-randomise if there is imbalance in treatment allocation on these variables. With a relatively small number of teams to allocate, we have decided to prioritise team type (within the local authority) to enable us to compare the impact of the programme on these subgroups.

Data collection

We have several data collection methods:

Impact evaluation

- Children and young people:
 - administrative data to measure children's social care involvement
- Social workers:
 - online survey to measure self-efficacy, stress
 - administrative data to measure sickness absence
- Foster/kinship carers:
 - online survey to measure self-efficacy

⁷ Due to a delay of the required data from Oxfordshire County Council, the randomisation was conducted for the three other local authorities first, and the teams from Oxfordshire County Council were allocated separately.

Sample size / MDES calculations

		MDES (Proportion of a Standard Deviation)
MDES		0.127
Proportion of variance in child's outcome explained by:	Child covariates (including baseline measure)	0.8
	Social Worker team covariates	0.1 (3 covariates)
Intraclass correlations (ICCs)	Team	0.03
Alpha		0.05
Power		0.8
One-sided or two-sided?		Two-sided
Level of intervention clustering		Social worker team
Average cluster size		150 children in each team
Sample Size (children)	Intervention	4500
	Control	4500
	Total	9000
Sample Size (teams)	Intervention	30 (15 per local authority)
	Control	30 (15 per local authority)
	Total	60

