MDES was determined by the Excel macro PowerUp⁸ for a 3-level fixed effects blocked cluster random assignment design with treatment at level 2 (BCRA3_2f). The three levels are individual (as we're detecting power for the primary outcome this is the child / young person), social worker team and local authority with treatment assigned at the social worker team level to 50% of the teams. One would not expect high intraclass correlation within teams themselves

⁸ Dong, N. and Maynard, R. A. (2013). *PowerUp!*: A tool for calculating minimum detectable effect sizes and sample size requirements for experimental and quasi-experimental designs. *Journal of Research on Educational Effectiveness*, 6(1), 24-67. doi: 10.1080/19345747.2012.673143

as cases aren't assigned to a team on the basis of similarity other than the level of social work involvement (child in need, child protection etc) (0.03). Baseline is expected to be highly predictive of endline SDQ score (0.8).

Outcome measures

The aim of Kitbag is to improve children's emotional literacy and ability to understand, express and regulate their emotions as well as improving their behaviour and relationships with others. The primary outcome measure is emotional and behavioural difficulties. The other outcomes are secondary outcomes.

Primary Outcomes

Child Outcomes

1i) Children's social care involvement

Given that we may have concerns about selection bias into the primary data collection, we shall also estimate the impact of the Kitbag programme on administrative outcomes which can be collected for all children and young people in the eligible population. Although children's social care administrative outcomes are more tangentially related to Kitbag and are also more difficult to change in a relatively light touch intervention, they have the benefit of not being subject to attrition bias. Kitbag will be delivered to children and young people with all levels of social work involvement, and the logic model does not suggest that it will be particularly beneficial for children and young people with particular children's social care profiles. The third secondary outcome measure is the level of children's social care involvement (2iii). Specifically, this is operationalised as the sum of escalations and de-escalations over the course of the intervention (May 2021 - May 2022):

- case closed
- child on child in need plan
- child on child protection plan
- child in care

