As represented in the logic model, one of the hypothesised mechanisms is carer self-efficacy. We measure parental / carer self-efficacy - “the parents’ beliefs about their effectiveness in overcoming or solving specific parenting problems” - using the parental self-efficacy subscale of the “Me as a parent” scale. The subscale consists of 4 questions and has been validated for parents of children aged 6 months to 15 years old. The subscale has good internal reliability (Cronbach’s alpha of .75), good test-retest reliability (.73), and good convergent validity (Pearson $r = .63$, $p.001$ between the 4 items of the MaaP self-efficacy subscale and the 8 items of the efficacy subscale of the 17-item Parent Sense of Competence scale²⁰). The questions will be adapted to account for those in non-parental caring roles. The population will be restricted to local authority employed foster carers only as these are the foster carers whom we will be able to access.

Analysis plan

Primary and Secondary Analysis

Primary analysis estimates the impact of the programme on our primary outcomes, whilst secondary analysis estimates the impact of the programme on our secondary outcomes. As the approach is the same, we outline it jointly below.

Models

The dependent variables are continuous and we will use an OLS regression. The regression coefficient on the treatment variable is interpreted as the impact of the intervention on the dependent variable (in the units described in the “Outcomes” section). Please see the “Outcomes” section for the expected direction of the impact.

¹⁸ Yankelovich, & Broadfoot, & Gillespie, Michael & Guidroz, Ashley. (2012). The Stress in General Scale Revisited: A One-factor Structure.. *Stress and Health*. 28. 137-148. The items (p.144) are Demanding, Pressured, Calm (R), Many things stressful, Nerve-wracking, Hassled, More stressful than I’d like, Overwhelming where (R) means reverse coded.

¹⁹ The Scale is usually calculated as the sum; however, we use the mean to allow for non-response.

²⁰ Hamilton, V. Matthews, J. & Crawford, S. (2014). Development and Preliminary Validation of a Parenting Self-Regulation Scale: “Me as a Parent”. *Journal of Child and Family Studies*. 24. 10.1007/s10826-014-0089-z.

Independent variable of interest: treatment

For the outcomes of social workers, family support workers and foster carers, treatment is coded as a binary variable where treatment = 1 if:

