Missing post-intervention data is a risk for this trial as some of the secondary outcomes are collected via primary data collection (an online survey) and the attrition is likely to be high given that the follow-up period is over a relatively long period of time (4 months - 12 months later) and the professionals may have left their employer.

Covariates

- If the covariate has more than 30% of the data missing, we will drop the covariate.
- For each covariate in the main model (see the “Covariates” section) that has up to 30% of the data missing, we will regress an indicator of missingness on the other covariates in the main model and outcomes using logistic regression, clustering the standard errors at the team level. If any of the coefficients on the covariates of the missingness model are statistically significant at the 5% level, then data is not missing completely at random (MCAR).
- To distinguish between whether the data is missing at random (MAR) i.e. missing conditional on observables or missing not at random (MNAR) i.e. missing conditional on unobserved variables, for all the covariates that were not MCAR we then impute the missing values of the covariate of interest (using a missing category for categorical variables and multiple imputation for numeric variables) and compare the treatment estimates using the imputed data and data restricted to the complete cases. If the results are similar (i.e. significant / insignificant, the same direction and only differing in magnitude of up to 20%), then data is likely to be missing at random (MAR). If the results are dissimilar, the data is likely to be missing not at random (MNAR).

If the data on covariates are MCAR or MAR, then complete case analysis is likely to be unbiased but less well powered. To maintain power we use a missing category for categorical variables as missingness is likely to be a predictor in itself and multiply impute missing numerical covariates (including pre outcome measures). We ignore the clustered structure of the data because cluster sizes are small, cluster follow-up rates may be highly variable and we expect the ICC to be low (we assume the ICC to be 0.03 in power calculations)²¹.

Outcomes

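### The MDES of 0.127 assumes equal teams of 150 children, 15 per authority; Tables 1 to 3 point to markedly unequal teams, and no allowance for this is made

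*Protocol*

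**What the plan says.** The Sample size / MDES calculations section states an MDES of 0.127 at 80% power, two-sided alpha 0.05. The design is a "3-level fixed effects blocked cluster random assignment design with treatment at level 2 (BCRA3_2f", with half the teams treated. Its inputs are a team ICC of 0.03, an R-squared of 0.8 for "Child covariates (including baseline measure", an R-squared of 0.1 for three team covariates, 60 teams and 9000 children. The row for average cluster size reads "150 children in each team". The rows for number of teams give 30 per arm, annotated as 15 per local authority. The Missing data strategy repeats the ICC: "we assume the ICC to be 0.03 in power calculations".

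Other parts of the protocol describe the teams differently.

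- **Design table:** the unit of randomisation is a "Social Work Team (6-8 social workers".
- **Table 1:** Bexley has 9 eligible teams, Haringey 11, Oxfordshire 30, and for Warwickshire the entry is "Total: 10 eligible teams".
- **Table 2:** under "Number of social workers and family support workers in teams in the intervention group" it lists 33, 28, 120 and 119 in the same order.
- **Table 3 (31 March 2020):** 1757, 2284, 4750 and 4073 children in need.

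On the analysis, the Models section says "The dependent variables are continuous and we will use an OLS regression". The Covariates, Standard errors and Regression specification sections add authority fixed effects and standard errors clustered by team. No weighting of teams is specified.

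**The concern.** The formula used has one cluster size and one number of teams per block, so it describes a balanced trial. The protocol's own tables do not. In an unweighted child-level regression each team counts in proportion to its number of children. When the between-team component dominates, extra children in a large team add almost no information, yet the large team still takes more weight. The precision claimed for equal teams is then not reached.

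At stake is the accuracy of the one figure that tells readers what size of effect the trial could reliably detect.

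**Working it through.** **1. The stated figure.** For BCRA3_2f with 4 authorities, 15 teams each and 3 team covariates, df = 4 × (15 − 2) − 3 = 49. The multiplier is 2.010 + 0.849 = 2.859.

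- Between-team variance: 0.03 × (1 − 0.1) = 0.027.
- Child-level variance per team: 0.97 × (1 − 0.8) / 150 = 0.194 / 150 = 0.0013.
- Var = (0.027 + 0.0013) / (0.25 × 60) = 0.001886, so SE = 0.0434.
- MDES = 2.859 × 0.0434 = 0.124. Power at 0.127 is P(T49 ≤ 0.127/0.0434 − 2.010), about 82%.

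This is within about 2% of 0.127, so the stated figure is reproduced for equal teams. The between-team part is 0.027 / 0.0283, or about 95% of the variance.

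**2. Team sizes implied by the tables** (Bexley, Haringey, Oxfordshire, Warwickshire).

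- Table 3 / Table 1: 1757/9 = 195, 2284/11 = 208, 4750/30 = 158, 4073/10 = 407 children in need per eligible team. Warwickshire is 2.0 to 2.6 times the others. Scaled to 9000 children: 137, 145, 111, 285; CV 0.41.
- Table 2 / half of Table 1: 33/4.5 = 7.3, 28/5.5 = 5.1, 120/15 = 8.0, 119/5 = 23.8 staff per intervention team. Warwickshire is 3.0 to 4.7 times the others. Scaled to 9000 children: 110, 76, 120, 357; CV 0.63.

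**3. Variance with unequal teams.** Let authority k have J_k teams of n_k children and a share w_k of all children. Then

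Var = Σ w_k² × [0.027/(0.25 J_k) + 0.194/(0.25 J_k n_k)],

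with J = 9, 11, 30, 10 and df = 49. All other inputs are as stated.

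| Team sizes | CV | Warwickshire's weight | SE | MDES | Power at 0.127 |
|---|---|---|---|---|---|
| Equal, 150 | 0 | 17% | 0.0434 | 0.124 | 82% |
| Proportional to Table 3 | 0.41 | 32% | 0.0468 | 0.134 | 76% |
| Proportional to Table 2 staff | 0.63 | 40% | 0.0509 | 0.146 | 69% |

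The shortcut agrees: 1 + CV² is 1.17 and 1.39, against exact variance ratios of 1.16 and 1.37.

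**4. Sensitivity to the number of treated Warwickshire teams.** The re-randomisation rule under Randomisation keeps the treated share of each team type between 0.25 and 0.75, except where there is a single team. For Warwickshire's 6 CIN/CPP, 1 CLA and 3 disability teams this allows 2–4, 0–1 and 1–2, so 3 to 7 in all. Table 2 sizes then give power of 55%, 63%, 69%, 73% and 75% for 3, 4, 5, 6 and 7 treated teams. Only the inferred team size changes here; the 50% allocation in the variance is kept.

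**5. Sensitivity to eligibility.** Table 3 counts all children in need. If Warwickshire's eligible share were 20% lower than elsewhere, the Table 3 version gives CV 0.30, MDES 0.129 and power 79%. At 30% lower it gives MDES 0.127 and power 80%. The 20% and 30% are assumptions.

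**6. Simulation of OLS with ordinary team-clustered standard errors** (4000 trials per setting). The empirical SEs were 0.043, 0.047 and 0.051 for equal, Table 3 and Table 2 sizes, matching the formula. Rejection at 0.127 was 83%, 79% and 73%, but under no effect it was 5.7%, 6.4% and 6.9%. Part of that apparent power is therefore excess type I error.

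**The case against.** The strongest reply is that nothing has been miscalculated and that the team sizes are guesses. Much of this stands. The figure is reproduced, and the cluster-size row is labelled an average, so the protocol never asserts equal teams; equality enters through the formula.

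A reader might infer that the trial has 69–76% power instead of 80%. The documents do not support so firm a statement. Table 3 includes children outside the eligible teams: about 12,900 in 2020 against about 9300 eligible. Warwickshire's only listed CLA team is for ages 14–18, so its eligible share may be lower, and step 5 shows that this could remove the shortfall between authorities. Table 2 was drawn up for Kitbag distribution and does not say how many teams were treated. Staff numbers are also an imperfect proxy for caseload.

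A reader might also infer that Warwickshire flatly contradicts the 6–8 in the Design table. That comparison is not like for like, because Table 2 adds family support workers. Still, even if all 10 Warwickshire teams were treated, 119 staff would be about 12 per team, while the same count gives about 5 to 8 elsewhere with half the teams treated. The entries need reconciling.

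It is fair to add that the trial's conclusions will rest on clustered standard errors that reflect actual team sizes, and that the protocol nowhere says a null result will be read through the planned MDES. The R-squared of 0.8 is justified by SDQ scores although the current primary outcome is escalations and de-escalations. That is a separate matter; the present point holds with every input left as stated.

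What remains is that the two proxies agree in direction, no allowance for unequal size is stated, and the entry of 15 teams per authority does not match Table 1.

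**Conclusion.** The point holds as an unsupported balance assumption, not as an arithmetic slip. Under the stated inputs and the planned child-weighted analysis, the MDES is likely to be above the 0.124 that equal teams give. Illustrative values are 0.134 (Table 3 sizes) and 0.146 (Table 2 sizes, 5 Warwickshire teams treated), a loss of about 6 to 13 points of power at 0.127. The plausible span is wider: 55–75% on staff counts across the permitted allocations, and up to about 79–80% on Table 3 if Warwickshire's eligible share is 20–30% lower.

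The results assume children per team proportional to staff or to children in need, half the teams treated (except where varied), and no size variation within an authority. Such variation would normally lower power further. The loss also depends on teams being weighted by caseload.

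**What to change.** Recompute the MDES from the actual or expected eligible caseload of each randomised team, either by summing over teams with the OLS weights or by multiplying the variance by about 1 + CV². Restate the MDES, or the power at 0.127, with the CV shown. Until caseloads are available, present 0.134–0.146 only as an illustration.

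In the same revision:

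- Replace the single 150 with a mean and range by authority.
- Replace the 15 per local authority with counts that agree with Table 1.
- Reconcile the 6–8 social workers with Table 2 on one staff definition, and state the number of treated teams per authority.

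This needs a recalculation and a wording change, with no additional teams or outcome data. The only downside is a less favourable stated MDES.
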